We will elicit perceptions of CVD risk alongside the collection of data on health and behaviours related to CVD, including utilization of preventive care. These data combined with the randomized provision of information on personal CVD risk will allow us to identify the impact of information on lifestyles, preventive care and intermediate health outcomes and how it operates through beliefs about susceptibility to CVD. This goes beyond policy simulations that rely on assumptions about the impact of information on beliefs. For example, from the estimated impact of beliefs about HIV on sexual activity, Delevande and Kohler (2016) infer that policy should target beliefs. But that prescription is valid only if beliefs are responsive to information. We can test this.

If it is confirmed that beliefs about CVD risks do respond to the provision of information on those risks, then we can use the exogenous variation in risk perceptions induced by the experiment to estimate the causal effect of beliefs on behaviour. This overcomes a fundamental problem of the endogeneity of beliefs arising from their dependence on past behaviour (Paula et al 2014). The information intervention provides an instrument for beliefs that identifies their impact on choices.

The data on beliefs give us an important advantage over most studies of the impact of information. They allow the mechanism to be traced. Information programs are often found to be ineffective in changing health behaviour. Usually, it is not known whether this is because the information did not shift beliefs or because any change in beliefs did not feed through to behaviour. If this experiment also produces a negative result, we will be able to identify at what stage the *theory of change* failed.

Primary prevention of CVD through the PEN

The PEN is founded on a substantial body of evidence that establishes the effectiveness of behavioural change (smoking cessation, weight loss, physical activity and reduced intake of salt and fat) and medication in preventing CVD. It is known that quitting smoking and taking antihypertensives, for example, reduce the risk of heart attack. The difficulty lies not in knowing what to do for someone at risk of CVD. Rather, it lies in identifying who is at risk and ensuring that they get the interventions that are known to be effective.

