D _T , D _C	Effect of base rate CVD risk information on perceived personal CVD risk.

F_T, D_C	Effect of information base rate + personal CVD risk information on
	perceived personal CVD risk.
H _T , H _C	Effect of base rate + personal + reduced risk factor CVD risk information
	on perceived personal CVD risk if reduced risk factors.
F_T - H_T , D_C - H_C	Effect of information on change in CVD risk if reduced risk factors on
	perception of that change.

- Using the treatment group only, we obtain an alternative estimate of the effect of being informed of predicted personal CVD risk on perceived personal CVD risk by regressing the latter on an indicator of whether it is measured prior to or after receiving personal risk information. That is, a simple before-after comparison: $p_i = x_i \beta + \gamma 1 (p_i = F_{Ti}) + u_i$, $p_i = D_{Ti}$ or F_{Ti} .
- We will run similar regressions to test for updating of confidence about reported risks and worry about CVD risk. See the last point under [H5a] on the relevance of the impact of information on belief confidence.

[H3b] Individuals who are exposed to the information intervention do not simply memorize numbers and percentages they are told in the treatment, but incorporate the information to update beliefs about event likelihoods related to CVD risks.

Test:

• Estimate the correlation between the prior-posterior change in perceived life expectancy and the prior-posterior change in perceived 10-year CVD risk. A negative correlation means that individuals update their life expectancy in a direction consistent with their revision to perceived personal CVD risk. For example, if the perception of CVD risk is raised, then life expectancy is reduced. We will repeat the same exercise for life expectancies conditional on experiencing a heart attack/stroke. As survival probabilities conditional on a CVD event are independent of CVD risk, a coefficient of zero is consistent with Bayesian updating. We use the same beliefs as described in [H3b] to test for updating following the provision of both base rate and personal CVD risks and the provision of only personal CVD risks.

[H3c] Updating of beliefs is heterogeneous with respect to education, predicted CVD risk, confidence about CVD risk estimates and worry about CVD events.

Test:

• Repeat regression (3.1) allowing λ to vary with the stated characteristics.

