[H3d] Updating of beliefs is asymmetrical in response to positive information, i.e. $prior_i > predicted_i$, and negative information i.e. $prior_i < predicted_i$.

Test:

• We run the following regression:

$$\begin{array}{l} (posterior_{i} - prior_{i}) = \lambda_{1i}(predicted_{i} - prior_{i}) \times 1(predicted_{i} \leq prior_{i}) + \lambda_{2i}(predicted_{i} - prior_{i}) \times 1(predicted_{i} > prior_{i}) + \varepsilon_{i} \end{array}$$

and test $\lambda_{1i} = \lambda_{2i}$ against $\lambda_{1i} > \lambda_{2i}$. That is, under the alternative hypothesis, individuals who receive good news respond more than those who receive bad news. Such asymmetric updating is

consistent with the reinforcement of optimism bias. However, in light of Harris and Hahn (2011) and Shah et al. (2016), we cannot infer a mechanism for optimism bias from $\lambda_{1i} > \lambda_{2i}$ alone.

Q4: Do beliefs about susceptibility to CVD affect behavior in relation to lifestyles and the demand for preventive care?

[H4a] Beliefs play an important role in determining health behavior. Individuals are forward-looking and take into account their perceived susceptibility to CVD in deciding on their use of primary prevention and health lifestyles. Further, they use perceptions of the response of CVD risk to risk factors when deciding whether to change health habits such as smoking and diet/exercise.

Test:

- Run regressions of the form, y_i = βx_i + θp̂_i + ε_i, where the dependent variable is an indicator of a) whether the person has attended a health facility for a checkup, including blood pressure measurement and diagnostic tests, b) whether is taking medication for hypertension/diabetes, c) smoking (at all and intensity), d) BMI, e) exercise and possibly others. In one set of regressions, p̂_i will be the predicted value of the perceived personal CVD risk, which will be obtained from of one of the regressions described under [H3a]. That is, in the first stage, perceived personal CVD risk measured after the giving the treatment group information on the base rate and their predicted personal risk is regressed on the treatment group indicator. The IV estimate of θ tells us how behaviour responds to changes in CVD risk perceptions induced by information on those risks.

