Individuals may be apprehensive of utilizing their beliefs about CVD risk because they lack confidence in the accuracy of those beliefs. Their beliefs are ambiguous. If individuals are ambiguity seeking in the loss domain, which is often found (Dimmock et al 2015), and are informed that their risks are lower than they had reported, then on gaining confidence in their downwardly revised beliefs they may become responsive to them. Being surer that the CVD risk is 15% rather than being very uncertain that it is 20% may cause an individual to adopt healthier behaviour.

Test:

• Repeat the regressions of the previous test but rather than including a single indicator of treatment group enter two indicators. One identifies respondents in the treatment group informed that their risk is above their initially reported risk. The other identifies respondents in the treatment group informed that their risk is at or below their reported risk. If it is only the correction of bias in risk perceptions that affects behaviour, then only the first group should adopt healthier behaviour. The second group, if anything, should adopt less healthy behaviour. If, to the contrary, the second group responds to the positive news they are given of their CVD risk by adopting healthier habits, this suggests an effect through reduced ambiguity. In addition, we will examine how the provision of information affects stated confidence in individuals' estimates of their risks of heart attack/stroke.

Q6: Is PhilPEN effective in delivering primary prevention of CVD to those who seek care at RHU/CHCs?

[H6a] As currently implemented, PhilPEN does not reduce the risk factor exposure and increase the medication of individuals with elevated CVD risk.

Test:

- Induce random variation in presentation for checkup at RHU/CHCs, which under PhilPEN are required to conduct CVD risk assessment of all patients, to screen those meeting specified criterion, to counsel all those screened on smoking cessation and to provide hypertension and diabetes medication to those at high risk defined by the WHO PEN protocol.
- The information intervention will not be used to generate this random variation since beliefs about CVD risk can impact on behaviour directly even without contact with health facilities and the PhilPEN program.

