- The likelihood insensitivity parameter, α_i , and the utility curvature parameter, r_i , will be identified for each individual *i* using their responses to hypothetical lottery (in gain domain) choice questions specifically designed for use in a survey context and previously used in the Philippines to estimate risk preferences (Van Wilgenburg et al., 2017).
- First, we will test whether compliance varies with a composite measure of risk aversion that comprises both utility curvature and likelihood insensitivity. Using r_i and α_i we will compute

each individual's certainty equivalent of the lottery (CE_i) , and subtract this from the expected value of the lottery (EV = 500) to get the risk premium R_i . This is calculated for all individuals irrespective of whether they are in the treatment group offered the lottery. $R_i > 0$ indicates risk aversion, $R_i < 0$ indicates risk loving and $R_i = 0$ is risk neutrality.

• We will estimate the following regression model,

$$s_i = \gamma Y_{it-1} + \beta x_{it-1} + \psi_1 L_i + \psi_2 R_i + \psi_3 L_i \times R_i + u_i.$$
(6.3)

- ψ_1 corresponds to the lottery response of risk neutral individuals.⁴ This will be positive if the expected gain from the lottery (500 PHP) is sufficient to bridge the shortfall of the expected health gain of the checkup from its cost. In the absence of the lottery incentive, this shortfall presumably explains why the individual does not go for a checkup. If the estimate of this parameter is not significantly greater than zero, we will learn that the perceived gains of a checkup fall short of the costs by more than 500 PHP.
- $\psi_3 < 0$ corresponds to greater compliance among more risk loving individuals.
- Because the estimates of the individual specific risk parameters, and so the risk premium, can be expected to be noisy, we will also try an alternative specification that enters binary indicators of whether the respondent is risk loving or risk averse (interacted with the lottery indicator) into the first stage regression, with risk neutral being the reference category.
- After having established whether compliance varies with a composite measure of risk attitudes, we will explore whether response to the incentive varies with utility curvature and likelihood insensitivity separately. We will estimate the following type of regression model,

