We will exclude from the study individuals who report that they have been diagnosed as having heart disease or diabetes, or who report that they have had a heart attack or a stroke. This is consistent with the study's focus on primary prevention of CVD. Those with heart disease, or who have had a heart attack or stroke, can benefit from secondary prevention. But examination of demand for and the effectiveness of such care would require another sampling strategy to identify a sufficiently large pool of potential beneficiaries. We exclude those with a diagnosis of diabetes because the office based version of Globorisk we will use substantially underestimates the 10-year CVD risk for those with diabetes.

Those currently (past 2 weeks) taking medication for hypertension will also be excluded because they are already receiving primary prevention of CVD. Respondents who report that they have been diagnosed with hypertension will be included provided they are not currently taking antihypertensives. Hence, those who are not adhering to this medication will be included in all components of the study. Those taking medication for diabetes will be excluded, although this should be a redundant exclusion criterion given those with a diagnosis of diabetes are excluded.

After completing a household roster to identify if there is anyone aged 40-70 and selecting one such person, there will be a short screening module to identify and eliminate anyone who meets the exclusion criteria defined in the previous two paragraphs. Also excluded will be those who have some medical problem that prevents measurement of blood pressure or BMI.

10. Power analysis

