Table 3 Estimates of intra cluster correlation coefficients for CVD risk factors at the level of primary care practices in North America

	Eastern Ontario	Rhode Island and Massachusetts	Vermont				
	Singh et al (2015)	Parker et al (2005)	Littenberg & MacLean $(2006)^{\pm}$				
Systolic Blood Pressure	0.054	0.047	0.042				
Low Density Lipoprotein	0.035	0.006	0.045				
Fasting Blood Glucose	0.023	0.016	N/A				
Body Mass Index	N/A	0.031	0.011				
Smoking	N/A	0.036	0.005				

 \pm Individuals with diabetes only.

For all other outcomes, we also assume an ICC of 0.1 in our baseline power calculations and test sensitivity to revising the value downward to 0.05.

Cluster size

We aim to observe 10 individuals within each cluster at follow-up who have been exposed to an intervention (or are in the control group). To achieve this, we sample a larger number at baseline to allow for attrition and non-eligibility for the lottery intervention. This cluster size is set to achieve a balance between constraining the sample size while limiting costs incurred by surveying in many barangays.

Autocorrelation in outcomes

We will estimate treatment effects using ANCOVA. That is, the post-treatment outcome observed at follow-up will be regressed on an indicator of treatment group membership and the pre-treatment outcome, plus covariates observed at baseline. The coefficient on the treatment indicator is the estimated treatment effect. For given power and minimal detectable effect size, the required sample size is decreasing with the autocorrelation of the outcome (as well as the proportion of its variance that can be explained using baseline values of covariates).

Estimates of the autocorrelation in predicted 10-year CVD risk are not available, as far as we are aware. Age, sex, smoking and BMI, four of the five predictors of CVD risk used by Globorisk, are obviously very highly autocorrelated. The fifth predictor -a single visit measure of blood pressure -can be

expected to display much lower serial correlation. Blood pressure can vary depending on recent activity and diet, although we will follow a standard protocol for its measurement. It may also vary with the enumerator, although this will be minimized by use of an electronic meter and we can control for enumerator effects.

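### H5b splits only the information arm by told risk versus own prior, so each coefficient mixes the information effect with a non-randomised difference between types of people

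*Combined protocol and SAP*

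**What the plan says.** H5b in Section 3.2 repeats the H5a regressions of behaviour on information-arm membership, with two indicators in place of one. "One identifies respondents in the treatment group informed that their risk is above their initially reported risk"; the other covers treated respondents whose told risk is at or below their report. No matching split of the controls is described. The plan then interprets the second coefficient: "If, to the contrary, the second group responds to the positive news they are given of their CVD risk by adopting healthier habits", this is taken to suggest an effect through less ambiguity.

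Other parts of the plan bear on this:

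- Table 1 shows that section D (own perceived risk) is asked in both arms. H2a regresses those answers on the Globorisk prediction in both arms, so controls have both components of the split.
- H4a supposes that people "take into account their perceived susceptibility to CVD in deciding on their use of primary prevention and health lifestyles". Section 3.1 warns of the "endogeneity of beliefs arising from their dependence on past behaviour".
- The dependent-variable table under H3a lists treated versus control section D answers as the "Effect of base rate CVD risk information on perceived personal CVD risk".
- Equation 6.3 enters the risk premium as a main effect beside its interaction with the lottery offer, so that the coefficient on the offer "corresponds to the lottery response of risk neutral individuals". Equation 6.4 does the same for its two risk parameters.
- Section 10.1 says the follow-up outcome will be "regressed on an indicator of treatment group membership and the pre-treatment outcome, plus covariates observed at baseline". The kinds of covariate it names do not include the prior or its gap from the prediction.

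**The concern.** The sign of predicted minus prior is a personal characteristic. People whose prior is at or above their prediction tend to hold high priors, and the others low ones. If priors are related to behaviour, the two types behave differently without any information. Comparing each treated type with a control group that contains both types puts that difference into the coefficient.

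The plan's own premises make such a relation plausible, with opposite signs. If higher perceived risk leads to healthier behaviour, as H4a holds, the at-or-below coefficient leans toward a false reduced-ambiguity reading. The above coefficient then leans toward harm, which could mask the healthier response expected there. If unhealthy behaviour raises perceived risk, as Section 3.1 allows, both signs reverse and a real ambiguity effect can be hidden.

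H5b reads the sign of a coefficient as evidence for a mechanism, and a larger sample does not shrink this bias.

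**Working it through.** **1. The plan's own sample size.** The documents give no figure for H5b, so I checked the arm sizes it would use. Table 6, mean CVD risk: difference 11.35 - 10.89 = 0.46, SD 11.35/5 = 2.27, 80% power, 5% two-sided (assumed).

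- Unadjusted n per arm = 2 x [(1.96 + 0.84) x 2.27/0.46]^2, about 383.
- Design effect 1 + 9 x 0.1 = 1.9; residual variance 1 - 0.36 = 0.64. 383 x 1.9 x 0.64 is about 466, rounded up to 47 clusters of 10 = 470.
- Control: 470/0.6^2 = 1,306. Information: 470/(2 - 0.36) = 287. Both match.

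The adopted sizes for binary outcomes, 299 and 1,361, follow in the same way from 490. I did not derive the 490.

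**2. What the H5b coefficients estimate.** Let q be the share of people whose prediction is above their prior. Let d be the expected outcome of that type minus that of the other type, given the covariates and without information. All controls together average q x d above the at-or-below type, so:

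- above coefficient = effect(above) + (1 - q) x d
- at-or-below coefficient = effect(at or below) - q x d

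Weighted by q and 1 - q, the bias terms cancel: q(1 - q)d - (1 - q)qd = 0. The pooled H5a contrast is therefore intact.

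**3. Illustrative size.** Assumptions that are not in the documents: prior mean 20%, SD 15; predicted SD 5.1 around the plan's mean of 11.35%; correlation 0.2; checkup rate 30%, changing by 0.3 to 0.5 points per point of prior; no information effect; baseline outcome correlated 0.6 with follow-up.

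Under these, the at-or-below group's mean prior lies 6.6 points above the overall mean and the above group's 13.3 below, so q = 6.6/(6.6 + 13.3) = 0.33. A baseline outcome correlated 0.6 leaves about 1 - 0.6 = 0.4 of the type difference:

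- at or below: 0.4 x 0.3 x 6.6 = +0.8; 0.4 x 0.5 x 6.6 = +1.3 points
- above: 0.4 x 0.3 x 13.3 = 1.6 and 0.4 x 0.5 x 13.3 = 2.7 points, both negative

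A cluster simulation (30 information and 136 control clusters of 10, ICC 0.1, cluster-robust errors, 1,500 to 2,000 trials per setting) agrees:

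| Slope | Above, as written | At or below, as written |
|---|---|---|
| 0 | -0.1 | 0.0 |
| +0.3 | -1.7 | +0.8 |
| +0.5 | -2.7 | +1.3 |
| -0.3 | +1.7 | -0.8 |
| -0.5 | +2.9 | -1.3 |

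With the indicator's main effect added, every entry is within 0.1 of zero.

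**4. Error rates** (nominal 2.5% in each direction).

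- At or below, SE 2.97: P(Z > 1.96 - 0.8/2.97) = 4.5% and P(Z > 1.96 - 1.3/2.97) = 6.4%. Simulated: 4.3-5.7%, and 2.2-2.4% after the fix.
- Above, SE 3.75: false harm 6.6% and 10.7% by the same formula. Simulated: 8.8-14.9%, and 3.2-4.8% after the fix.
- Reverse slope, for an assumed real 8-point benefit at or below: power is P(Z < 8/3.06 - 1.96) = 74% after the fix. As written it is P(Z < 7.2/2.97 - 1.96) = 68% or P(Z < 6.7/2.97 - 1.96) = 62%. Standard errors from those simulation settings put all three about 3 points higher.

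**5. Where the baseline outcome does not help.** With no useful baseline, the at-or-below bias is 0.3 x 6.6 = 2.0 to 0.5 x 6.6 = 3.3 points, with false healthier signals in 6.7-11.1% of trials. Antihypertensive medication is such an outcome, because under Section 9 "Those currently (past 2 weeks) taking medication for hypertension will also be excluded", so the baseline value is constant. At Table 5's 10% rate and slopes of 0.1 to 0.2, the simulated bias is +0.7 to +1.2 points.

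**6. Sensitivity.**

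- Predicted SD 2.27, as in Section 10.1: +0.9 to +1.4 points and 4.5-6.2%.
- Slope 0.5 (above, at or below): prior mean 10, SD 10 gives (-1.1, +2.2); prior mean 35, SD 20 gives (-5.8, +0.7); baseline correlation 0.4 gives (-4.2, +2.2).
- The main setting implies d of about 0.05 to 0.09 SD (2.4 to 4.0 points over an SD of about 46). Were d larger, with q = 0.5, the two-sided false-positive rate would be 9% at 0.1 SD and 23% at 0.2 SD.

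**7. The split variable itself.** The treated section D answer follows base-rate information and the control answer does not. If that information lowers treated answers by 20%, the at-or-below bias is +1.0 to +1.7 as written and +0.2 to +0.3 after the fix. If by 40%, it is +1.3 to +2.5 and +0.5 to +1.2. Splitting both arms on section B stays within 0.1 of zero (assumed correlation of section B with the prior, 0.5).

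**The case against.** The bias is modest where the mechanism claim is made: +0.8 to +1.3 points against an SE of 2.97 is 0.27 to 0.44 of a standard error. The larger figures need a baseline outcome that does not help, although the plan intends to adjust for one. Every driver of the size is assumed, and the sign is unknown. The covariate list is open and wide, so the residual difference could be smaller than shown, and adjusting for the prior is not ruled out. Part of the false-harm excess is not this bias, since the rate stays at 3.2-4.8% after the fix, and H5b draws no harm conclusion from that coefficient. The section D fix is incomplete if base-rate information moves the treated answers. H5b is one cautiously worded secondary test, with a randomised comparison of stated confidence beside it.

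All of this stands as a limit on size and scope. It does not answer the structural point: the prior is not among the covariates named, the baseline outcome removes only part of the difference and none of it for medication, and the plan uses the correct form in equations 6.3 and 6.4.

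**Conclusion.** The concern holds. Followed as written, H5b yields coefficients that are not information effects unless the two types behave alike given the covariates. That follows from the design and needs no assumption about size. The size and direction cannot be known from the documents. With the assumed belief distributions, the bias in the coefficient that carries the mechanism claim is about 1 point either way with a useful baseline outcome, and 2 to 3 points without one. It can therefore suggest reduced ambiguity where there is none or hide it where it exists. This should be fixed before analysis. It does not touch H5a, the comparison of stated confidence between arms, the principal outcome or Table 6.

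**What to change.** - Define A = 1 if the Globorisk prediction exceeds the section D answer and 0 otherwise, in both arms. Fit y = βx + a·A + θ1·I·A + θ2·I·(1 - A) + e, where I is the information arm, and read the two information effects from θ1 and θ2. This follows equations 6.3 and 6.4.
- State that this split is approximate, because the treated section D answer follows base-rate information and the control answer does not.
- Add a sensitivity analysis that splits both arms on section B (perceived versus predicted base rate), which is asked before any information. State that it classifies error about the base rate and not personal news.
- State that the baseline outcome is included wherever one exists.

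The cost is analysis wording only, since all variables are already collected in both arms. The standard error rises from 2.97 to 3.06 points for the at-or-below effect (about 3%) and from 3.75 to 3.98 for the above effect (about 6%). With an even split, power for 0.2 SD in each half falls from a nominal 67% to 65%. H5b is therefore below 80% power for that effect under either form, and the plan should say so.
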